12.4.2 Biochemical Abnormalities during Treatment

Table 12.4.2.1 Biochemical abnormalities, worst grade per patient.

Table 12.4.2.2 Biochemical abnormalities, worst grade per cycle.

Tables 12.4.2.1 and 12.4.2.2 will have the following pattern but depending on the number and severity of the adverse events observed, the NCI-CTCAE v4 grades may be grouped as ≥ 1 and ≥ 3 categories.

	Grade 1		...	Grade 4		Grade ≥ 1		Grade ≥ 3	
	N	%	...	N	%	N	%	N	%
AST increased									
ALT increased									
Total bilirubin increased									
AP increased									
Hyperglycemia									
Hypoglycemia									
...									

Note: Tables 12.4.2.1 and 12.4.2.2 also for s1 and s2.

Listing 12.4.2.3 Grade ≥ 3 biochemical abnormalities. Worst grade per patient.

Patient id.	Test	Grade

Listing 12.4.2.4 Grade ≥ 3 biochemical abnormalities. Worst grade per cycle.

Patient id.	Cycle	Test	Grade

Listing 12.4.2.5 Biochemical tests not assessed by patient and cycle.

Patient id.	Total number of cycles	Cycle with missing lab. test	Lab. test

12.4.3 Coagulation Abnormalities during Treatment

Table 12.4.3.1 Coagulation abnormalities, worst grade per patient.

Table 12.4.3.2 Coagulation abnormalities, worst grade per cycle.

Tables 12.4.3.1 and 12.4.3.2 will have the following pattern but depending on the number and severity of the adverse events observed, the NCI-CTCAE v4 grades may be grouped as 1-3 category.

	Grade 1		...	Grade 3		Grade ≥1		Grade ≥3	
	N	%		N	%	N	%	N	%
INR increased									
APTT prolonged									

Listing 12.4.3.3 Grade 3 coagulation abnormalities. Worst grade per patient.

Patient id.	Test	Grade

Listing 12.4.3.4 Grade 3 coagulation abnormalities. Worst grade per cycle.

Patient id.	Cycle	Test	Grade

Listing 12.4.3.5 Coagulation tests not assessed by patient and cycle.

Patient id.	Total number of cycles	Cycle with missing lab. test	Lab. test

12.4.4 Laboratory Values over Time

Table 12.4.4.1 Evolution of hematological abnormalities from baseline, worst case per patient.

Table 12.4.4.2 Evolution of hematological abnormalities from baseline, worst case in the first cycle per patient.

Table 12.4.4.3 Evolution of biochemical abnormalities from baseline, worst case per patient.

Table 12.4.4.4 Evolution of biochemical abnormalities from baseline, worst case in the first cycle per patient.

Tables 12.4.4.1 to 12.4.4.4 will have the following pattern:

		Baseline grade*	Worst grade per patient						Total	
			0		1		...		N	%
			N	%	N	%	N	%		
Baseline	Parameter 1	Grade 0								
		Grade 1								
									
	Parameter 2	Grade 0								
		Grade 1								
									
	Grade 0								
		Grade 1								
									

(*) Defined as the last value recorded before or on the date of first infusion.

Table 12.4.4.5 Platelet count time course pattern (summary).

Table 12.4.4.6 Neutrophil count time course pattern (summary).

Tables 12.4.4.5 and 12.4.4.6 will have the following pattern:

	All cycles	First cycle
	N, Mean, Std., Median, Range	N, Mean, Std., Median, Range
Grade $\geq 3^*$ onset day		
Nadir ($\times 10^9/L$)		
Duration of grade ≥ 3 (days)		
Day of recovery to grade 1/2 or baseline values**		

(*) Grade 3 or 4; (**) grade 2 or less.

Table 12.4.4.7 AST time course pattern (summary).

Table 12.4.4.8 ALT time course pattern (summary).

Tables 12.4.4.7 and 12.4.4.8 will have the following pattern:

	All cycles	First cycle
	N, Mean, Std., Median, Range	N, Mean, Std., Median, Range
Grade $\geq 3^*$ onset day		
Peak ($\times ULN$)		
Duration of grade ≥ 3 (days)		
Day of recovery to grade 1/2 or baseline values**		

(*) Grade 3 or 4; (**) grade 2 or less.

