6.5 CRITERIA FOR TREATMENT CONTINUATION

Further treatment cycles (i.e., Cycle 2 or subsequent) will be administered every q3wk (± 48 hours) if the patient fulfills all the re-treatment criteria defined in [Table 6](#).

Table 6. Criteria for treatment continuation.

Variable	Re-treatment (Day 1)
ECOG PS	≤ 2
Hemoglobin*	≥ 8.0 g/dl
ANC	≥ 1.5 × 10 ⁹ /l
Platelets	≥ 100 × 10 ⁹ /l
AST/ALT	≤ 3.0 × ULN
Total bilirubin or direct bilirubin	≤ 1.5 × ULN or × ULN
Albumin	≥ 3 g/dl
Serum creatinine	≤ 1.5 × ULN or creatinine clearance ≥ 30 ml/min
CPK	Grade ≤ 1
Other non-hematological drug-related AEs (except isolated increased GGT and/or AP; grade 2 asthenia, constipation, alopecia, peripheral neuropathy, or non-optimally treated nausea and/or vomiting)	Grade ≤ 1
Active infection (including sepsis) and/or bleeding (any grade)	Absence

* Patients may receive packed red blood cells (PRBC) transfusion and/or erythropoietin (EPO) treatment, if clinically indicated, to increase/maintain adequate hemoglobin levels.

AE(s), adverse event(s); ANC, absolute neutrophil count; AP, alkaline phosphatase; AST/ALT, aspartate aminotransferase/alanine aminotransferase; CPK, creatinine phosphokinase; ECOG, Eastern Cooperative Oncology Group; GGT, gamma-glutamyltransferase; PS, performance status; ULN, upper limit of

Variable	Re-treatment (Day 1)
----------	----------------------

normal.

If a patient does not meet the requirements for re-treatment on Day 1 of any following cycle, regardless of the reason, re-assessments will be performed at least every 48-72 hours. Treatment will be then withheld, up to a maximum of three weeks beyond its due date, until appropriate recovery.

Patients not meeting re-treatment criteria after a maximum 3-week delay must be withdrawn from trial. In case of objective clinical benefit, the patient could continue receiving the treatment (upon the Sponsors' agreement).

For any delay due to treatment-related adverse events lasting for more than one week, a dose reduction must be implemented upon recovery, following the rules explained in the next section (Section 6.6).

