7.2 Clinical Laboratory Evaluation

Laboratory results will be classified according to the NCI-CTCAE v4.

The following hematological values (worst grade per patient and per cycle during treatment) will be displayed: white blood cells count (WBC), neutrophils count, lymphocytes count, platelets count and hemoglobin.

Overall cross tabulation will be presented for the worst grade during treatment *versus* the baseline severity grading of leukopenia, neutropenia, lymphopenia, thrombocytopenia and anemia.

If a grade ≥ 3 neutropenia or thrombocytopenia occurs during a cycle of treatment, the first day it reaches grade 3 or 4 (counting from the start of the cycle) and the duration of the abnormality (i.e., until recovery to grade ≤ 2) will be tabulated.

Similarly, the following biochemical values (worst grade per patient and per cycle during treatment) will be displayed: alanine aminotransferase (ALT), aspartate aminotransferase (AST), total bilirubin, alkaline phosphatase (AP), creatine phosphokinase (CPK), creatinine, gamma-glutamyltransferase (GGT), calcium (corrected by albumin levels), potassium, sodium, magnesium, glucose and albumin.

If a grade ≥ 3 AST or ALT increase occurs during a cycle of treatment, both the day it peaked (counting from the start of the cycle) and the duration of the abnormality (i.e., until recovery to grade ≤ 2) will be tabulated.

Overall cross tabulation will be presented for the worst grade during treatment *versus* the baseline severity grading of biochemical abnormalities.

7.3 Vital Signs, Physical Examination, Left Ventricular Ejection Fraction and Electrocardiogram Findings

Tabulation will be made summarizing the performance status, body weight, left ventricular ejection fraction (LVEF) and electrocardiogram (ECG) abnormalities at baseline and during the treatment, if appropriate, for each cohort and patient.

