8.9 Imputation of Incomplete Dates

The dates of certain historical or on-study clinical data are key components for statistical analysis. An incomplete date results from a missing day, month or year; in that case, the missing figure can be imputed, thus allowing the calculation of variables, such as duration and time of a specific event. However, when all dates (day, month and year) are missing, no imputation will be done unless otherwise specified. Whenever imputations are applicable, it will be clearly specified in the corresponding shell table, listing or figure in sections 10-16 of this SAP.

Before Registration

If the day of a month is unknown, then the imputed day will be the 1st. of the month; if the month is also unknown, then the imputed date will be the 1st of July. This assumption will only be valid if the imputed date occurs earlier than the first dose administration date; otherwise the imputed date will be the first day of the month of administration of the first dose (i.e. 01/ month of administration of the first dose/year).

Between treatment start and end of treatment

All date variables during treatment where information is needed and is not fully available, for example adverse events or concomitant medications, will be subject of imputation by means of SAS programming. If the day of a date is unknown then the imputed day will be 1, if the month and/or year is also unknown then the imputed date will 1/January (this assumption will be valid if the imputed date is later than the treatment start date; otherwise, the imputed date will be the treatment start date).

After End of Treatment

To ensure the most conservative approach for the time-to-event variables (i.e., DR, PFS and OS), which can be affected by missing values, the following rules will be implemented: if the day of a date is unknown then the imputed day will be the 1st; if the month is also unknown, then the imputed date will be the 1st of July. This assumption will be valid if the imputed date occurs later than the last drug administration date; otherwise the imputed date will be the date of the last drug administration plus the predefined cycle length (i.e., 21 days if PM01183), except if the patient dies before, in which case the date of death minus 1 will be used. For OS, if a patient dies the imputation event date should be the last date the patient is known to be alive minus one day.

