8.12 Methods for Handling Missing Data

Missing values will be tabulated with their frequency but they will not be included in the calculation of percentages.

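### SAP Tables 12.4.4.5–12.4.4.8 summarise duration of, and day of recovery from, grade 3 or higher laboratory abnormalities in recovered episodes only, so both rows read somewhat short (minor)

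*SAP*

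**What the plan says.** For neutropenia and thrombocytopenia of grade 3 or higher, SAP 7.2 tabulates the first day the grade is reached "and the duration of the abnormality (i.e., until recovery to grade" 2 or less). The same end point is given for AST and ALT. No other way for an episode to end is stated.

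The shells in SAP 12.4.4 (Tables 12.4.4.5–12.4.4.8) have four rows: onset day, nadir or peak, duration, and "Day of recovery to grade 1/2 or baseline values". The last is footnoted as grade 2 or less. Each row is filled with "N, Mean, Std., Median, Range", once for all cycles and once for the first cycle. No row or footnote deals with episodes that had not recovered.

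Three other rules bear on this:

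- SAP 8.9 says that "when all dates (day, month and year) are missing, no imputation will be done unless otherwise specified", and adds that "Whenever imputations are applicable, it will be clearly specified in the corresponding shell table, listing or figure". The 12.4.4 shells specify none.
- SAP 8.12 says: "Missing values will be tabulated with their frequency but they will not be included in the calculation of percentages".
- SAP 6.2.2 plans Kaplan-Meier for DR, PFS and OS only.

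On follow-up, Protocol 6.5 says: "Patients not meeting re-treatment criteria after a maximum 3-week delay must be withdrawn from trial". Protocol 7.5 lets follow-up of a treatment-related event stop at stabilisation or at the start of new antitumor therapy.

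**The concern.** Duration is a time to event, and some episodes will lack the event. A patient may die, start another therapy, or leave treatment with the value still at grade 3 or higher. Under the stated definition these episodes have no duration and no recovery day, and a plain mean or median passes over them.

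The loss is not random. Re-treatment requires the ANC, platelet and AST/ALT criteria to be met, so an episode followed by a further cycle has normally recovered. The missing values collect in last cycles and lean towards long episodes. The first-cycle column is exposed too, for patients whose first cycle was their last.

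At stake is how reversibility is described. Protocol 1.10.1.3 calls neutropenia in the earlier phase I work generally short-lasting. A reader will look to these tables to see whether that holds here.

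**Working it through.** The plan gives no figure for these rows, so there is nothing to reproduce. The direction follows from the definitions; the size can only be illustrated.

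**Assumed inputs (not in the documents)**
- Recovery time T is exponential with mean m = 7 or 10 days.
- Onset is uniform on days 8–15. Protocol 1.10.1.3 places the nadir, not the onset, in the second week.
- A share w = 0.2 or 0.5 of episodes falls in the last cycle; the rest are fully observed.

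**Two ends of observation**
- Day 30: the nominal end-of-treatment visit (Protocol 5.8).
- Day 42: a 21-day cycle plus the three-week maximum delay (Protocol 6.5).

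**Formulas.** Observation after onset is uniform from a to b, with b − a = 7. For day 30, a = 15 and b = 22; for day 42, a = 27 and b = 34.

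- Unrecovered share of last-cycle episodes: S = (m/7)(e^(−a/m) − e^(−b/m))
- Mean among those that recover: R = m − K/(1 − S), with K = (m/7)[(a+m)e^(−a/m) − (b+m)e^(−b/m)]
- Pooled mean with unrecovered episodes left out: [(1−w)m + w(1−S)R] / (1 − wS)
- Fall in the pooled median: m·ln(1 + wS), valid because the medians lie below a

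**Worked case (day 30, m = 7).** S = 0.1173 − 0.0432 = 0.074. K = 22 × 0.1173 − 29 × 0.0432 = 1.33. R = 7 − 1.33/0.926 = 5.56. With w = 0.2 the pooled mean is (5.6 + 0.2 × 0.926 × 5.56)/(1 − 0.0148) = 6.73, a fall of about 4%.

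| Observed to | m | S | R | Pooled mean, w = 0.2 | Pooled mean, w = 0.5 | Fall in median (w = 0.2 / 0.5) |
|---|---|---|---|---|---|---|
| Day 42 | 7 | 1.3% | 6.6 | 6.92 (−1%) | 6.80 (−3%) | <0.1 / <0.1 d |
| Day 42 | 10 | 4.8% | 8.5 | 9.71 (−3%) | 9.25 (−7%) | 0.1 / 0.2 d |
| Day 30 | 7 | 7.4% | 5.6 | 6.73 (−4%) | 6.31 (−10%) | 0.1 / 0.3 d |
| Day 30 | 10 | 16.0% | 6.5 | 9.40 (−6%) | 8.42 (−16%) | 0.3 / 0.8 d |

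**If unrecovered episodes are cut at the last sample instead.** The pooled mean is m(1 − wS). It is low by 0.3–2.4% at day 42 and 1.5–8.0% at day 30. In this model the median does not move, because every cut value is at least 15 days.

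**Check with earlier loss of follow-up.** In a separate simulation, last-cycle observation ended uniformly 1–20 days after onset, as early death or new therapy might cause. It used true means of 4, 7 and 14 days, exponential or Weibull (shape 1.5) recovery, and last-cycle shares of 20, 50 and 100%. In all 18 scenarios the mean and median were low, whether episodes were left out or cut. For an exponential mean of 7 days, leaving them out gave 6.57 at a 20% share and 5.82 at 50%, against 6.99: falls of 6% and 17%.

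**The case against.** The best reply is that the loss is small and visible.

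- **Testing is intensive.** Protocol 5.7 repeats relevant tests at least every 48–72 hours until grade 2 or less after a related grade 3 or higher event. Protocol 6.5 reassesses delayed patients on the same rhythm. Protocol 5.8 repeats values that were grade 2 or higher at the end-of-treatment visit, and Protocol 5.9 follows ongoing related events every four weeks. This stands, and it makes the day-42 rows more plausible for patients still under observation. It does not help when death or new therapy ends observation early.
- **The gap shows.** Each row has its own N, and SAP 8.12 counts missing values, so onset N minus recovery N reveals a shortfall. This stands in part: the difference does not separate non-recovery from a missed test, and it does not correct the mean or median.
- **A rule may exist elsewhere.** SAP 8.15 refers to a separate conventions document, which is not available here. That exclusion is the outcome is therefore an inference from SAP 7.2 and 8.9 together. But the tables cite no such rule, and SAP 8.9 says imputations will appear in the shell.
- **Kaplan-Meier is optional for a descriptive table** with repeated episodes per patient, and censoring at new therapy may be informative. Both are fair. They are reasons for a footnote, not for leaving the count out.

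A reader might infer more than the documents support:

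- **That the most serious toxicity disappears from the report.** It does not. Onset day and nadir or peak stay in the same tables. The episodes also appear in the worst-grade tables (SAP 12.4.1 and 12.4.2) and in the laboratory and adverse event listings.
- **That reported durations are 20–35% short.** Falls of that size (7 to 5.6, 10 to 6.5) arise only among last-cycle episodes with a day-30 stop, not in the pooled column.
- **That re-treatment guarantees recovery, or that withdrawal after a delay means a persisting grade 3 value.** Protocol 6.5 allows continuation for objective clinical benefit, and the criteria can also fail on performance status, albumin, CPK or infection.

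**Conclusion.** The point holds as a minor one. As written, the duration and day-of-recovery rows describe only episodes seen to recover. Both natural defaults, leaving the others out or cutting them at the last sample, shorten the mean duration.

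The true size cannot be computed, because neither the unrecovered share nor the distribution of durations is given. The 1–7% (day 42) and 4–16% (day 30) falls in the pooled mean rest on exponential recovery with mean 7–10 days, onset on days 8–15 and a 20–50% last-cycle share. Shorter true durations would make the bias smaller; earlier loss of follow-up would make it larger. Neutropenia timing is also carried over to AST and ALT, for which the documents give none.

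No test, stopping rule or response analysis depends on these rows.

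**What to change.** In SAP 7.2 and Tables 12.4.4.5–12.4.4.8:

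1. Add a row for episodes not recovered to grade 2 or less at the last sample (n, %). This is the minimum change.
2. Report the Kaplan-Meier median time from the first grade 3 or higher value to recovery to grade 2 or less, beside or in place of the plain mean and median. Censor unrecovered episodes at the last laboratory sample. Count death without recovery as not recovered, keeping the episode in the risk set rather than censoring it at death.
3. State in a footnote that censoring at new therapy may be informative and that the all-cycles column can include several episodes per patient.
4. Make the recovery row label agree with its own footnote and with SAP 7.2.

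The cost is a little programming and slightly longer reported durations. No new data are needed.

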12.5 Physical Findings, PS, LVEF, ECG and Other Tests

Each table, listing and figure displayed in this section will have a comprehensive header identifying the tumor type (cohort) or the total population (if applicable).

12.5.1 Physical Findings and PS (ECOG)

Listing 12.5.1.1 ECOG performance status during the study.

	Cycle/ECOG PS*						
	0	1	2	3	4	...	EOT
Patient id.							
...							
...							

(*) Worst ECOG PS score of the cycle determinations.

Listing 12.5.1.2 Weight by patient per cycle.

	Cycle/Weight						
	0 (kg)	1* (%)	2* (%)	3* (%)	4* (%)	...* (%)	EOT* (%)
Patient id.							
...							
...							

(*) % of changes compared to baseline.

12.5.2 LVEF, ECG and Other Related Tests

Listing 12.5.2.1 Patients with abnormal or clinical indicated LVEF during the study.

Patient id.	Assessment date	Abnormality	Specify	Reason for clinically indicated	Method	LVEF (%)	Institution normal range

Listing 12.5.2.2 Patients with abnormal or clinical indicated Electrocardiogram during the study.

Patient id.	Assessment date	Result	Specify	Reason for clinically indicated repeat	PR interval (msec)	Heart rate (bpm)	QT interval (msec)	QRS complex (msec)	QTc Fridericia	QTc* (Bazett's)

(*) QTc (Bazett's) = QT interval / $\sqrt{(60/\text{Heart rate})}$.

12.6 Concomitant Therapy / Procedures According to the ATC Classification.

Each table, listing and figure displayed in this section will have a comprehensive header identifying the tumor type (cohort) or the total population (if applicable).

Table 12.6.1 Concomitant medication during treatment (ATC1/ATC2/ATC3/ATC4/PN).

Concomitant medication	N	%
Alimentary tract and metabolism		
Antacids		
Magnesium compounds		
Magnesium adipate		
...		
Blood and blood forming organs		
Antithrombotic agents		
Vitamin K antagonists		
Acenocoumarol		
...		

Table 12.6.2 Summary of concomitant medication during treatment.

	N	%
No. of systems (ATC1 level)		
0		
1		
2		
≥ 3		
Mean, Standard Deviation, Median (Range)		
No. of indications (ATC2 level)		
0		
1		
2		
≥ 3		
Mean, Standard Deviation, Median (Range)		
No. of agent families (ATC4 level)		
0		
1		
2		
≥ 3		

Mean, Standard Deviation, Median (Range)		
No. of agents (PN level)		
0		
1		
2		
≥ 3		
Mean, Standard Deviation, Median (Range)		

Table 12.6.3 Patients and cycles with any transfusions/GCSF during treatment.

	N	%
No. of patients with Platelet transfusions		
No. of cycles with Platelet transfusions		
No. of patients with RBC		
No. of cycles with RBC		
No. of patients with GCSF		

Note: Also for s1 and s2.

Listing 12.6.4 Patients with any transfusion during treatment.

Patient id.	Cycle	PM1183 dose in the previous cycle	Platelets / RB	Date of first transfusion	Date of last transfusion	No. of units required*

(*) No. of transfusions for platelets or No. of packed RBC transfusions.

Listing 12.6.5 Patients with GCSF during treatment.

Patient id.	Cycle	Date	Medication	Reason	Specify

12.7 Subsequent therapy.

Table 12.7.1 Any Subsequent medical therapy.

	N	%
Type		
Medical therapy		
Radiotherapy		
Surgery		
Number of subsequent medical therapies (Median and range)		
0		
1		
2		
...		
Subsequent agents of medical therapy (ATC)		
...		
...		

Note: Also for s1 and s2.

Table 12.7.2 First Subsequent medical therapy.

	N	%
Subsequent chemotherapy agents (ATC)		
...		
...		

Note: Also for s1 and s2.

Table 12.7.3 First Subsequent medical therapy. Best response (if available).

Best response	First Subsequent therapy

		CR	PR	SD	PD	NE
PM01183	CR					
	PR					
	SD					
	PD					
	NE					

Note: Also for s1 and s2; (*) If a low number of best responses to the subsequent therapy are available, a listing, instead of this table, will be provided. In case of sufficient number of subsequent Immunotherapy, a separate table/listing will be performed for patients having immunotherapy as first subsequent therapy.

Table 12.7.4 First Subsequent medical therapy. PFS (if available).

PFS (months)		First Subsequent therapy				
		<1 month	[1-3) months	[3-6) months	[6-12) months	≥12 months
PM01183	<1 month					
	[1-3) months					
	[3-6) months					
	[6-12) months					
	≥12 months					

Note: Also for s1 and s2;

Any other exploratory analyses will be performed at the analysis time if any relevant variable will be considered potentially relevant. Table's layout will follow the same prior patterns.

12.8 Subgroup Analyses Related to Safety.

Table 12.8.1 Worst grade ≥ 3 by patient in special subgroups (Sex).

Table 12.8.2 Worst grade ≥ 3 by cycle in special subgroups (Sex).

Table 12.8.3 Worst grade ≥ 3 by patient in special subgroups (Age*).

Table 12.8.4 Worst grade ≥ 3 by cycle in special subgroups (Age*).

Table 12.8.5 Worst grade ≥ 3 by patient in special subgroups (Race).

Table 12.8.6 Worst grade ≥ 3 by cycle in special subgroups (Race).

Table 12.8.7 Worst grade ≥ 3 by patient in special subgroups (Number of prior lines*).

Table 12.8.8 Worst grade ≥ 3 by cycle in special subgroups (Number of prior lines*).

Table 12.8.9 Worst grade ≥ 3 by patient in special subgroups (BSA*).

Table 12.8.10 Worst grade ≥ 3 by cycle in special subgroups (BSA*).

Table 12.8.11 Worst grade ≥ 3 by patient in special subgroups (ECOG).

Table 12.8.12 Worst grade ≥ 3 by cycle in special subgroups (ECOG).

Table 12.8.13 Worst grade ≥ 3 by patient in special subgroups (Geographical area*).

Table 12.8.14 Worst grade ≥ 3 by cycle in special subgroups (Geographical area*).

Table 12.8.15 Worst grade ≥ 3 by patient in special subgroups (AAGP*).

Table 12.8.16 Worst grade ≥ 3 by cycle in special subgroups (AAGP*).

Tables 12.8.1 to 12.8.16 will have the following pattern:

Laboratory abnormalities/ drug-related AEs	Subgroup 1			Subgroup 2				
	No. of patients/cycles evaluated	Grade ≥ 3	%	No. of patients/cycles evaluated	Grade ≥ 3	%	No. of patients/cycles evaluated	Grade ≥ 3	%
Thrombocytopenia									
Neutropenia									
AP									
Bilirubin									
AST									

[figure not shown]
Laboratory abnormalities/ drug-related AEs	Subgroup 1			Subgroup 2				
	No. of patients/cycles evaluated	Grade ≥ 3	%	No. of patients/cycles evaluated	Grade ≥ 3	%	No. of patients/cycles evaluated	Grade ≥ 3	%
ALT									
CPK									
Nausea									
Vomiting									
Fatigue									
Other**									

(*) Categories Age (<65 yrs vs ≥ 65 yrs); Number of prior lines (1 line vs ≥ 2 lines); BSA (≤ 1.8 m² vs. > 1.8 m²) Geographical area (Europe vs US); Alpha-glycoprotein (ULN \leq vs $>$ ULN). (**)Any drug-related toxicity present in $\geq 5\%$ of patients in any group.

13 Figures

[figure not shown]
Figures displayed in this section will have a comprehensive header identifying the tumor type (cohort) or the total population (if applicable) and/or any other specific subgroups (e.g: CTFI categorized). See examples below, numbering will be updated accordingly.

Figure 13.1.1 Waterfall graph by subgroup.

Waterfall for each tumor type will be also provided. Also SCLC by CTFI (RR, R, S VS).

[figure not shown]
Figure 13.1.2 Waterfall graph by IRC (SCLC cohort).

Waterfall for SCLC and by CTFI (RR, R, S VS).

[figure not shown]
NOTE: If the measurements of the first and the second radiologists are the same, the target lesions measurements of the first one will be selected. If the measurements of both radiologists are different and an adjudicator is involved, his/her endorsement will be selected.

Figure 13.1.3 Pattern of hematological/non-hematological abnormalities per tumor type.

[figure not shown]
Hematological abnormalities include neutrophils and platelets; non-hematological abnormalities include AST and ALT.

Figure 13.1.4 Best response, PFS and Reasons for discontinuation (SCLC cohort).

[figure not shown]
Also for s1 and s2.

Figure 13.1.5 Last previous TTP vs PFS PM01183 (SCLC cohort).

[figure not shown]

Note: For PM01183 responders and/or SD (if applicable)

Figure 13.1.6 Last previous Immunotherapy TTP vs PFS PM01183 (SCLC cohort).

[figure not shown]

Figures described in **Section 11.3 Efficacy Analysis** will have the following patterns depending on the number of groups represented:

Number of patients at risk

299	286	254	231	207	187	170	145	134	123	112	102	92	82	70	59	47	37	27	16	12	7	5	4	3	3	2
-----	-----	-----	-----	-----	-----	-----	-----	-----	-----	-----	-----	----	----	----	----	----	----	----	----	----	---	---	---	---	---	---

Number of patients at risk

	0	3	6	9	12	15	18	21	24	27	30	33	36	39	42	45	48	51	54	57
Group A	166	156	141	129	115	100	88	77	65	52	43	32	24	14	7	5	4	3	3	
Group B	153	112	90	66	55	38	35	29	27	21	16	9	3	1						

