8.3 Baseline and Demographic Data

Baseline data such as demographics, cancer history, prior therapy, prior relevant history, signs and symptoms, ECG, LVEF, physical examination, vital signs, laboratory values and concomitant medication, coded according to the World Health Organization (WHO) Anatomical Therapeutic Chemical (ATC) classification system, will be described following standard tables detailed in Appendix I.

Age, baseline weight, height, and body surface area (BSA) will be summarized descriptively.

Baseline weight and height will be recorded on the case report form (CRF).

Baseline BSA will be calculated using the Dubois & Dubois formula.

Age categories and race will be summarized with frequency counts.

Baseline Eastern Cooperative Oncology Group (ECOG) performance status (PS) will be summarized with frequency counts.

For the cancer history: time from initial diagnosis, time from metastatic disease and time from last progression before the study entry will be recorded. These time calculations will be shown in months and summarized descriptively. Histology and characteristics of the disease at study entry will be tabulated.

Previous relevant medical history (other than cancer) will be listed.

A frequency tabulation of the number of patients with and the different types of previous surgery, radiotherapy, or therapy (number of lines) will be given.

Adverse events at baseline will be displayed by tabulation of frequencies according to NCI-CTCAE v4 toxicity grades. They will also be listed.

In case of pre-treatment characteristics with multiple measurements per patient before the start of treatment (e.g. laboratory assessments, vital signs) the baseline measurement will be considered the last valid value prior to or on the first day of treatment.

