8.10 Decimal Places

By default, all numeric results will be rounded to one decimal, except when variables are integers; in that case, they will be reported without decimals (for example, age in years, number of sites, etc.). Three decimal places will be used for Hazard Ratios or Odds Ratios. Four decimal places will be used for p-values.

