8.11 Subgroup Analyses

Specific subgroup efficacy analyses will be done for patients with SCLC. These analyses will be performed by IA/IRC and in all evaluable/all treated patient populations, pre-specified analyses are by CTFI defined as the time from the last dose of the last platinum containing therapy to the occurrence of progressive disease,(< 90 days and \geq 90 days and/or Refractory (RR) [$<$ 30 days], Resistant (R)[\geq 30 and $<$ 90 days], Sensitive (S) [\geq 90 and $<$ 180 days] and Very Sensitive (VS)[\geq 180 days]), excluding patients with CTFI $<$ 30 days and considering event to clinical progressions although they

were not documented by radiological images. Any other exploratory analyses requested by the physician at the time of the analysis will be clearly explained, specifying the selected patient population and following the same layout detailed for the other subgroup analyses.

If the number of patients recruited in any cohort differs at least 10% from the sample size assumptions, a sensitivity analysis for main efficacy endpoints using all evaluable patients will be performed.

Pre-specified safety subgroup analyses are: by sex (male vs. female), by age (<65 years-old vs. ≥65 years-old), by race (white vs. other), by number of prior lines (1 vs. >1 line), by BSA (<1.8 vs. ≥1.8) and by geographical area (USA vs. Europe vs. rest of the world).

No differentiation by center is planned.

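### The category footnote for the SAP 12.8 safety tables omits the rest-of-world region that SAP 8.11 pre-specifies, and places a BSA of exactly 1.8 m² in the opposite group

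*SAP*

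**What the plan says.** SAP 8.11 (Subgroup Analyses) lists the pre-specified safety subgroups. For region it gives "by geographical area (USA vs. Europe vs. rest of the world"), and for body surface area "by BSA (<1.8 vs. ≥1.8").

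SAP 12.8 (Subgroup Analyses Related to Safety) lists the tables. BSA is in Tables 12.8.9 and 12.8.10, and region in Tables 12.8.13 and 12.8.14. All four carry an asterisk. One shell serves the whole set: "Tables 12.8.1 to 12.8.16 will have the following pattern". The asterisked footnote under that shell defines the categories as "BSA (≤ 1.8 m² vs. > 1.8 m²") and "Geographical area (Europe vs US").

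Three other parts of the SAP bear on the point:

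- SAP 4.3 and the opening of SAP 12 base safety on the All Treated Patients set, by cohort and in total, with no exclusion or pooling by region.
- SAP 8.3 states: "Baseline BSA will be calculated using the Dubois & Dubois formula". It says nothing about rounding before patients are grouped.
- SAP 8.10 states: "By default, all numeric results will be rounded to one decimal", with exceptions. It does not say whether this applies to a derived variable before it is categorised.

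**The concern.** The methods section and the output specification define the same two subgroups differently, and a programmer normally works from the shell and its footnote. Followed to the letter, the footnote gives region tables with two categories. A treated patient from any other region would belong to neither, and the two denominators would not add up to the treated population. A reader of the report could take the tables for the complete regional breakdown promised in 8.11.

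For BSA the cut-point is the same but the equality sign sits on opposite sides, so a patient at exactly 1.8 m² is in the upper group under 8.11 and the lower group under 12.8.

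What is at stake is whether a few grade 3 or higher frequency tables are complete and reproducible. No hypothesis test or stopping rule uses them.

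**Working it through.** The plan gives no figure to reproduce here, so the check is a comparison of the two current definitions.

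**All footnoted subgroups that also appear in 8.11**

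| Subgroup | SAP 8.11 | SAP 12.8 footnote | Same partition? |
|---|---|---|---|
| Age (years) | <65, ≥65 | <65, ≥65 | Yes |
| Prior lines | 1, >1 | 1, ≥2 | Yes, since lines are whole numbers |
| BSA | <1.8, ≥1.8 | ≤1.8, >1.8 m² | No, differs at 1.8 |
| Region | USA, Europe, rest of the world | Europe, US | No, one category missing |

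The conflict is confined to BSA and region.

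**Region.** Let N be the number treated and N_E, N_U and N_R the numbers from Europe, the USA and elsewhere.

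- Under 8.11 the categories cover N_E + N_U + N_R = N.
- Under the footnote they cover N_E + N_U = N − N_R.
- The shortfall is N_R. The documents give no accrual by country or region, so N_R is unknown. It is zero if every treated patient comes from Europe or the US. Table 10.1.7 will tabulate accrual by country and institution, so N_R can be derived at analysis.

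**BSA.** Let B be baseline BSA.

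- Lower group under 8.11: B < 1.8. Lower group under 12.8: B ≤ 1.8.
- The two differ only for B = 1.8 exactly.
- B is calculated from height and weight by formula. If it is grouped unrounded, an exact tie at 1.8 is very unlikely, so almost nobody changes group.

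Rounding before grouping would create ties. As an illustration only, assume B is normal with mean m and standard deviation s, neither of which is in the documents, and round to two decimals. The share at 1.80 is Φ((1.805 − m)/s) − Φ((1.795 − m)/s). With m = 1.8 and s = 0.2 this is Φ(0.025) − Φ(−0.025) ≈ 0.020, or 2.0%. Over m = 1.7 to 1.9 and s = 0.15 to 0.25 it runs from 1.5% to 2.7%. This is a reason to state the precision, not an estimate of what will happen.

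**The case against.** **The shell has room for a third region.** This is correct. The common pattern shows Subgroup 1, Subgroup 2 and a further open block with its own count and percentage columns. A reader might infer that the tables have no place for rest-of-world patients, and the shell does not support that. But the block is generic to all sixteen tables, while the footnote names the categories and names only two. Appendix I lets layouts change to suit cohort size, which does not extend to category definitions.

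**The footnote may be the later and deliberate choice.** The SAP version history records the three-region sentence entering 8.11 in Section 15.2 and the footnote categories entering in Section 15.3. However, the 8.11 sentence recorded in 15.2 had a BSA cut of 2 and the current one has 1.8, so 8.11 was revised after that entry. Section 15.4 records a further edit to 8.11, the definition of the chemotherapy-free interval. Three regions remain in the current text. The chronology does not show that the third region was abandoned.

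**A reader might infer that the one-decimal default in SAP 8.10 moves a sizeable share of patients across the BSA cut.** That default concerns numeric results, and nothing says it applies to BSA before grouping.

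**A reader might also infer that the ECOG and AAGP tables are not pre-specified, since 8.11 omits them.** They are listed in SAP 12.8 itself, and 8.11 does not claim to be exhaustive. That is an incomplete cross-reference with no effect on results.

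**These are descriptive tables.** Agreed, and that limits how much the point matters.

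**Conclusion.** The inconsistency is real and minor. Two current parts of the SAP define the region and BSA safety subgroups differently, with no rule of precedence.

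Region is the part that matters. Read literally, the 12.8 footnote leaves treated rest-of-world patients uncategorised in Tables 12.8.13 and 12.8.14. The number affected cannot be taken from the documents and may be zero, so a claim that a substantial group will be lost is not supported. No patient leaves the main safety analysis.

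The BSA mismatch is negligible on the unrounded calculated value and needs only tidying. The conclusion rests on the wording of the two sections and on the footnote being programmed as written. It does not depend on any assumed accrual or BSA distribution.

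**What to change.** In the SAP 12.8 footnote, replace the two regions with the three in 8.11 and use the open third block of the existing shell, so that every treated patient falls in a category. Use one BSA inequality in both sections. Since the footnote is being edited anyway, the simplest course is to adopt the form in 8.11. State in one of the two places that the cut is applied to the unrounded calculated baseline value.

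The cost is one footnote and one short clause. No new data are needed, because country is already tabulated by site, and nothing changes in the sample size, the efficacy analyses or the other safety tables. It is best done before the tables are programmed.
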